8.2.3. Sensitivity Estimands of the Primary Endpoint

Three sensitivity estimands will be analyzed to support the evaluation of the primary objective.

Table 8: Sensitivity Estimands of Primary Objective

Variable: Time to development of CL-RA	
Estimand Label: Sensitivity 1.1	
Population: mITT	IES Policy 2
Population Level Summary: Same as Primary 1.0	Analysis: Same as Primary 1.0
Estimand Label: Sensitivity 1.2	
Population: PP	IES Policy 1
Population Level Summary: Same as Primary 1.0	Analysis: Same as Primary 1.0
Estimand Label: Sensitivity 1.3	
Population: PP	IES Policy 2
Population Level Summary: Same as Primary 1.0	Analysis: Same as Primary 1.0

8.3. Secondary Objectives

The secondary objectives for the ARA08 study and the analyses to evaluate them are provided in this section. Planned analyses described in the subsections below are based on the mITT

population. If warranted, analyses may be repeated on the PP population at the discretion of the study team.

8.3.1. Study Objective 2

Study Objective 2 is to evaluate the impact of HCQ on development of CL-RA in high-risk participants 12 months after initiation of study treatment. The clinical endpoint to evaluate this objective will be the development of CL-RA at 12 months. Details on the derivation of the development of CL-RA are provided in section 8.2.1.

Table 9: Estimand of Study Objective 2

Variable: Time to development of CL-RA	
Estimand Label: Secondary 2.1	
Population: mITT	IES Policy 1
Population Level Summary: Estimated risk at 12 months for each treatment arm and the difference between the treatment arms (with 95% confidence intervals) will be derived from Kaplan-Meier (KM) curves and using the Greenwood formula for estimating the variance.	Analysis: The analysis will be based on the KM estimated risk of CL-RA at 12 months, where risk = (1-KM estimated probability of “survival”). Survival for this analysis is defined as absence of CL-RA. Estimated risks will be derived from a Kaplan-Meier curve using censored time-to-event data to account for attrition under the assumption of non-informative censoring. The test statistic will be a Wald-type chi-square statistic derived by dividing the difference of the logit-transformed KM survival estimates for each arm by the associated variance derived using the delta-method. (Klein, et al. 2007) [2]

8.3.2. Study Objective 3

Study Objective 3 is to evaluate the impact of HCQ on development of IA, that may or may not meet criteria for RA, in high-risk participants 12 months after initiation of study treatment. The clinical endpoint to evaluate this objective will be the development of inflammatory arthritis (IA) at 12 months.

IA is defined as the development of swollen joint(s) consistent with RA-like synovitis. The joint exams conducted at each clinic visit will be used to identify the presence of swollen joints due to IA.

Table 10: Estimand of Study Objective 3

Variable: Time to development of IA	
Estimand Label: Secondary 3.1	
Population: mITT	IES Policy 1
Population Level Summary: Estimated risk at 12 months for each treatment arm and the difference between the treatment arms (with 95% confidence intervals) will be derived from Kaplan-Meier (KM) curves and using the Greenwood formula for estimating the variance.	Analysis: The analysis will be based on the KM estimated risk of IA at 12 months, where risk = (1-KM estimated probability of “survival”). Survival for this analysis is defined as absence of IA. Estimated risks will be derived from a Kaplan-Meier curve using censored time-to-event data to account for attrition under the assumption of non-informative censoring. The test statistic will be a Wald-type chi-square statistic derived by dividing the difference of the logit-transformed KM survival estimates for each arm by the associated variance derived using the delta-method. (Klein, et al. 2007) [2]

8.3.3. Study Objective 4

Study Objective 4 is to evaluate the impact of a 12-month course of HCQ on the timing of development of CL-RA over the entire study period. The clinical endpoint to evaluate this objective will be the development of CL-RA through 36 months. Details on the derivation of the development of CL-RA are provided in section 8.2.1.

Table 11: Estimands of Study Objective 4

Variable: Time to development of CL-RA	
Estimand Label: Secondary 4.1	
Population: mITT	IES Policy 1
Population Level Summary: Kaplan-Meier (KM) survival curves (with 95% confidence intervals) will be estimated from baseline through Month 36 for each treatment arm.	Analysis: The analysis will be based on the KM survival curves for time to CL-RA from baseline through 36 months. Survival for this analysis is defined as absence of CL-RA. Time-to-event data are censored under the assumption of non-informative censoring. The log rank test will be used to compare HCQ vs. placebo.
Estimand Label: Secondary 4.2	
Population: mITT	IES Policy 1
Population Level Summary: Estimated hazard ratios (and 95% confidence intervals) associated with the treatment effect derived from the Cox proportional hazards model.	Analysis: A Cox proportional hazards model will be fit with covariates for site (Colorado vs. other sites) and method of recruitment, along with treatment interactions. Only interaction terms with p-values<0.05 will be retained in the model. Wald chi-square tests will be used generate p-values associated with HRs for the treatment effect. Note: The validity of the proportional hazards assumption will be evaluated.
Note: Originally, the method of Lee, Wei, and Amato (Lee, et al. 1992) [3] was planned to estimate HRs for the treatment effect from the marginal Cox models for clustered data under assumptions of independent and exchangeable correlation structures to account for familiar clustering. However, familial cluster was not an issue for this study, so only the traditional Cox proportional hazards model will be performed.	
Estimand Label: Secondary 4.3	
Population: mITT	IES Policy 1
Population Level Summary: Kaplan-Meier (KM) survival curves (with 95% confidence intervals) will be estimated from baseline through Month 36 for each group defined by site (Colorado vs other) and treatment arm.	Analysis: The analysis will be based on the KM survival curves for time to CL-RA from baseline through 36 months. Survival for this analysis is defined as absence of CL-RA. Time-to-event data are censored under the assumption of non-informative censoring. Log rank tests will be used to compare HCQ vs. placebo, and to compare the Colorado study site vs. all other study sites within each treatment arm.

8.3.4. Study Objective 5

Study Objective 5 is to evaluate the impact of a 12-month course of HCQ on the timing of development of IA, that may or may not meet criteria for RA, over the entire study period. The clinical endpoint to evaluate this objective will be the development of inflammatory arthritis (IA) through 36 months.

Autoimmunity Centers of Excellence
 Statistical Analysis Plan – ARA08 StopRA

IA is defined as the development of swollen joint(s) consistent with RA-like synovitis. The joint exams conducted at each clinic visit will be used to identify the presence of swollen joints due to IA.

Table 12: Estimands of Study Objective 5

Variable: Time to development of IA	
Estimand Label: Secondary 5.1	
Population: mITT	IES Policy 1
Population Level Summary: Kaplan-Meier (KM) survival curves (with 95% confidence intervals) will be estimated from baseline through Month 36 for each treatment arm.	Analysis: The analysis will be based on the KM survival curves for time to IA from baseline through 36 months. Survival for this analysis is defined as absence of IA. Time-to-event data are censored under the assumption of non-informative censoring. The log rank test will be used to compare HCQ vs. placebo.
Estimand Label: Secondary 5.2	
Population: mITT	IES Policy 1
Population Level Summary: Estimated hazard ratios (and 95% confidence intervals) associated with the treatment effect derived from the Cox proportional hazards model.	Analysis: A Cox proportional hazards model will be fit with covariates for site (Colorado vs. other sites) and method of recruitment, along with treatment interactions. Only interaction terms with p-values<0.05 will be retained in the model. Wald chi-square tests will be used to generate p-values associated with HRs for the treatment effect. Note: The validity of the proportional hazards assumption will be evaluated.
NOTE: Originally, the method of Lee, Wei, and Amato (Lee, et al. 1992) [3] was planned to estimate HRs for the treatment effect from the marginal Cox models for clustered data under assumptions of independent and exchangeable correlation structures to account for familiar clustering. However, familial cluster was not an issue for this study, so only the traditional Cox proportional hazards model will be performed.	
Estimand Label: Secondary 5.3	
Population: mITT	IES Policy 1
Population Level Summary: Kaplan-Meier (KM) survival curves (with 95% confidence intervals) will be estimated from baseline through Month 36 for each group defined by site (Colorado vs other) and treatment arm.	Analysis: The analysis will be based on the KM survival curves for time to IA from baseline through 36 months. Survival for this analysis is defined as absence of IA. Time-to-event data are censored under the assumption of non-informative censoring. Log rank tests will be used to compare HCQ vs. placebo, and to compare the Colorado study site vs. all other study sites within each treatment arm.

8.3.5. Study Objective 6

Study Objective 6 is to explore the relationship between baseline and evolving symptoms, risk factors and the development of future CL- RA and response to HCQ. Baseline RA symptoms include self-reported joint pain, stiffness, and swelling, and overall fatigue. Risk factors include but are not limited to age, sex, genetic factors, socio-economic status, education, tobacco exposure, medications and medical hormone use, and dietary factors. The clinical endpoint to evaluate this objective will be the development of CL-RA through 36 months. Details on the derivation of the development of CL-RA are provided in section 8.2.1.

Table 13: Estimand of Study Objective 6

Variable: Time to development of CL-RA	
Estimand Label: Secondary/Exploratory 6.1	
Population: mITT	IES Policy 1
Population Level Summary: Hazard ratios (HRs) associated with potential risk factors and modifiers to the HR for the treatment effect comparing HCQ vs. placebo will be estimated with 95% CIs based on a Cox proportional hazards model.	
Analysis: In the first step in the analysis, fixed effect characteristics of participants who developed CL-RA will be compared to those who did not develop CL-RA during the study using descriptive (e.g., means (SD) or n (%)) and inferential statistics (e.g., Mann-Whitney or Fisher-type exact statistics) appropriate for the nature of the variable.
 
In the next step, the impact of potential risk factors on the development of RA and modification of the treatment effect will be explored using a Cox proportional hazards model. To identify a subset of risk factors for possible inclusion in a final model, we will first run preliminary models each with one potential risk factor, treatment, and the treatment*risk factor interaction. Risk factors with p-values <0.1, and interaction terms with p-values <0.05 will be considered for the final model. The same criteria for inclusion will be used for the final model. Interaction terms will be evaluated first, dropping least significant terms one-by-one until only interactions with p<0.05 remain. Fixed effect components of interaction terms will be included in the final model regardless of p-value. For other fixed effect terms, least significant terms will be dropped one-by-one until only terms with p<0.1 remain. Note: The validity of the proportional hazards assumption will be evaluated.
 
Finally, if results of analyses described in Section 8.3.6, Study Objective 7 or Section 8.3.7, Study Objective 8 suggest that evolving symptoms or risk factors are potentially related to the development of CL-RA, we will consider adding time-varying covariates to the model developed above. The modeling approach will follow that outlined above. Time-varying covariates must be carefully defined prior to modeling, and models must be interpreted with caution.
 
Note: The time-varying covariate model will be exploratory and only undertaken if warranted by results of other analyses.

Fixed effects (i.e., potential risk factors) to be evaluated include:

- Study site (Colorado vs other sites)
- Method of recruitment (FDR, Population-based screening, rheumatology clinic)
- Baseline self-reported joint pain
- Baseline self-reported joint stiffness
- Baseline self-reported joint swelling
- Baseline self-reported fatigue
- Baseline CDAI
- Baseline SDAI
- Baseline RAPID-3
- Baseline DAS28-CRP

Autoimmunity Centers of Excellence
Statistical Analysis Plan – ARA08 StopRA

- Baseline PROMIS Profile 29 Physical Health Score
- Baseline PROMIS Profile 29 Mental Health Score
- Baseline PROMIS Profile 29 Social Health Score
- Baseline Anti-CCP3 (units)
- Baseline Anti-CCP3 Positivity (Negative (< Upper Limit of Normal (ULN), Low Positive (1.0 - <2.0 x ULN), Medium Positive (2.0 - <3.0 x ULN), High Positive (\geq 3.0 x ULN))
- Baseline IgM-RF (U/mL)
- Baseline IgM-RF Positivity (Negative (< Upper Limit of Normal (ULN), Low Positive (1.0 - <2.0 x ULN), Medium Positive (2.0 - <3.0 x ULN), High Positive (\geq 3.0 x ULN))
- Baseline hs-CRP (mg/L)
- Baseline hs-CRP Positivity (\leq 3.0 mg/L, $>$ 3.0 mg/L)
- Baseline age (years)
- Sex (male/female)
- BMI
- Baseline Shared Epitope (SE) Positivity (Yes, No)
- Baseline Shared Epitope Number of Positive Results (0, 1, 2)
- Participant has a FDR with RA (Yes, No)
- Salary level (< \$50,000; \$50,000 - < \$75,000; \geq \$75,000)
- Highest education level achieved (up to High School/GED, College, Graduate School)
- Tobacco exposure
 - Smoking status (Never smoked, Former smoker, Current smoker)
 - Baseline Pack Years at Current Level for Smokers
 - Years as Adult Living with Smoker
- Baseline Medications
 - Statin use (Yes/No)
 - Medical hormones (Yes/No)

Each fixed effect will be evaluated for its impact on the time to development of CL-RA by fitting a Cox proportional hazards model with independent variables for treatment arm, risk factor and treatment arm * risk factor interaction. The risk factors with significant p-values for the Wald chi-square test statistic, along with significant interaction terms, will be included in the final Cox proportional hazards model.

8.3.6. Study Objective 7

Study Objective 7 is to evaluate the relationship between treatment with HCQ and amelioration of symptoms of RA, and potential delay in onset of symptoms. RA symptoms include self-reported joint pain, stiffness, and swelling, and overall fatigue. The clinical endpoint to evaluate this objective will be the self-reported joint symptom counts assessed at each clinic visit.

Participants use the Participant Self-Reported Joint Symptoms assessment to identify painful, stiff, and swollen joints. These data are used to count the number of (1) painful, (2) stiff, and (3) swollen joints, as well as the count of (4) painful, (5) stiff, and (6) swollen joints in the hands, wrists, and feet.

Table 14: Estimands of Study Objective 7

Estimand Label	Variable
Secondary 7.1	Number of self-reported painful joints at each clinic visit
Secondary 7.2	Number of self-reported stiff joints at each clinic visit.
Secondary 7.3	Number of self-reported swollen joints at each clinic visit
Secondary 7.4	Number of self-reported painful joints in the hands, wrists, and feet at each clinic visit
Secondary 7.5	Number of self-reported stiff joints in the hands, wrists, and feet at each clinic visit
Secondary 7.6	Number of self-reported swollen joints in the hands, wrists, and feet at each clinic visit
Population: mITT	IES Policy: All available study data will be included.
Population Level Summary: At each planned clinic visit, the number, and percent of individuals with self-reported joint symptoms will be computed by treatment arm, and separately for those with and without a prior study-confirmed diagnosis of CL- RA. Among those with symptoms, mean, median, min and max # of affected joints will also be reported. Summary statistics will also be plotted over time to gain a better understanding of trends.	Analysis: At Week 52 and Month 36/EOS, Mann-Whitney U statistics will be used to compare joint counts between treatment arms, separately for those with and without a diagnosis of CL-RA. Because the distributional characteristics of these variables are unknown, we cannot prespecify the planned analysis strategy. However, in this population, it is reasonable to expect there will be excess # of participant visits where no joint symptoms are reported. If this is the case, it may appropriate to fit a longitudinal zero-inflated negative binomial model with the number of involved joints as the dependent variable and treatment arm as the primary fixed effect. Important additional fixed effects to consider would include prior CL-RA diagnosis at time of assessment (Y/N), study day (or visit), treatment period (on study drug vs off study drug), duration on study treatment, and interaction terms for treatment arm, prior CL-RA diagnosis, and study day (or visit). Heterogeneous random participant effects could be included in the model per the methods of Zhu et al [4], and relevant covariates included in the regression on the covariance matrix will be determined. T-tests for the maximum likelihood estimates of the model parameters could be used to determine the significance of the parameters to the model.
Note: Modeling will be exploratory and only initiated if descriptive analyses suggest interesting trends.	

8.3.7. Study Objective 8

Study Objective 8 is to explore underlying immune responses over time in the early natural history of RA development and in response to HCQ therapy through measurement of a variety of biomarkers. Endpoints will be laboratory test results from mechanistic specimens collected at specified clinic visits during the study.

Table 15: Estimands of Study Objective 8

Estimand Label	Biomarkers and immune response variables
Secondary 8.1	Levels of anti-CCP3 over time
Secondary 8.2	Levels of IgM-RF over time
Secondary 8.3	Levels of hsCRP over time
Population: mITT	IES Policy: All available study data will be included.
Population Level Summary: Summary statistics and plots will be used to gain an understanding of the data prior to developing any statistical models or hypothesis tests.	Analysis: Inferential analyses will be considered if descriptive analyses suggest interesting trends.

For categorical variables, frequencies and percents will be computed at each time point by treatment group and separately by participants who were or were not diagnosed with CL-RA.For continuous variable, the number, mean (SD), median, min, and max score will be computed at each planned clinic visit, by treatment arm, and separately for those with and without a prior study-confirmed diagnosis of CL-RA. If any continuous variables that have values below the limit of detection, dichotomous variable will be created and summarize.Summary statistics will also be plotted over time to gain a better understanding of trends.	
Note: All mechanistic data is generated by core laboratory facilities, which may also run analyses.	

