1.5.4 Rationale for the Inclusion Criteria

The goal of the inclusion criteria is to identify subjects that are at high-risk for developing IA and clinically-apparent RA within 3 years. As discussed above, there are numerous genetic and environmental risk factors for RA; however, while it is intriguing to consider genetic and environmental factors in the prediction of RA, there is not clear data to date that evaluating genetic and environmental factors adds substantial predictive power to future RA beyond that of anti-CCP positivity. In particular, Bos et al. demonstrated that within anti-CCP positive subjects, the presence of the SE was not associated with increased risk for progression to RA [85]. As such, genetic factors including the presence of the SE as well as environmental exposures will be assessed in this study, although these factors will not be used in the development of inclusion/exclusion criteria.

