3.1.1 Stratification, Randomization, and Blinding

Subjects will be randomized in a 1:1 ratio to either HCQ or placebo. As some study sites may only randomize a few subjects, an adaptive randomization procedure based on Pocock and Simon[165] minimization concepts will be used to increase the likelihood of balance between treatment arms on key factors associated with progression to clinically-apparent RA. The key factors will include smoker status (smoker vs. non-smoker), study site, and method of recruitment (i.e. FDR, general population, or clinic screening. For additional detail on recruitment strategies, see Section 4.3, *Strategies for Recruitment and Retention*).

To maintain the study blind, the appearance of the study treatments, HCQ and placebo, and their packaging will be identical. Clinical staff will be blinded to the treatment assignments until completion of the study with the exception of an unblinded pharmacist. In addition, clinical staff members, including the investigators, will not have access to any mechanistic data, and mechanistic laboratory staff will not have access to any clinical results until completion of the study.

An individual's treatment assignment will only be unblinded if the subject experiences a suspected adverse reaction that is serious and unexpected (see Section 7.2.2, *Adverse Reaction and Suspected Adverse Reaction* and Section 7.2.3, *Unexpected Adverse Reaction*) or other protocol-specific event(s) determined by DAIT/NIAID to warrant unblinding.

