8.3.1.2 Secondary Efficacy Analyses

All secondary analyses will be conducted in an exploratory fashion with p-values and confidence intervals presented as descriptive statistics with no adjustments for multiple comparisons. Tests will be two-sided and interval estimates will be generated at the 95% confidence level. All efficacy analyses will be repeated using the PP population.

The KM estimates for the two arms will be compared using the log-rank test, and survival at 12 months will be compared using methods analogous to those described for the primary efficacy analysis. The two arms will also be compared after control of appropriate covariates using a Cox proportional hazards model. The modeling will also evaluate the relationship between time to onset of clinically-apparent RA (or IA) and covariates such as site, method of recruitment, age, sex, race, baseline characteristics, genetic and environmental factors, and biomarkers.

Treatment group comparisons of longitudinal changes in secondary efficacy endpoints, including disease activity scales, subject self-evaluation scores, and patient reported outcome scores (See Section 3.3.1, *Secondary Efficacy Endpoints*) will be evaluated using repeated measures random regression models. Models will be fit to allow piece-wise fixed-effect for time during the 12-month treatment period and during the subsequent follow-up period through 36 months. A random slope and intercept will be fit for each subject assuming an unstructured covariance matrix. Additional models may be developed to evaluate the relationship of endpoints with appropriate covariates.

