8.5.2 Multi-center Studies

As noted above, analyses of survival estimates at fixed points in time will not be stratified. Site and method of recruitment will be included as fixed covariates in models for secondary efficacy analyses. All safety analyses will be based on pooled data with no adjustment or stratification.

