7.2. Randomization

Participants were randomized in a 1:1 ratio to either HCQ or placebo. Anticipating that some study sites would only randomize a few participants, an adaptive randomization procedure based on Pocock and Simon [1] minimization concepts was used to increase the likelihood of balance between treatment arms on key factors associated with progression to clinically-apparent RA. The factors used in the adaptive randomization procedure were smoker status (smoker vs. non-smoker), study site, and method of recruitment (i.e., first degree relative (FDR), general population, or clinic patient). Participants with elevated anti-CCP levels that met assay positivity criteria were identified for this trial through three general approaches that included the following:

- Pre-screening FDRs of patients with RA.
- Health-fair, biobank, or other population-based pre-screening.
- Identification in rheumatology clinics of participants with ACPA positivity in the absence of IA.

These three participant pools provided a sampling of the types of participants for whom this preventative approach would be applicable.

To avoid possible issues of familial correlation, our strong preference was to randomize only 1 FDR per family. Participants were asked about participation of immediate family members during the consent process and during study participation. However, recognizing operational

Autoimmunity Centers of Excellence
Statistical Analysis Plan – ARA08 StopRA

barriers to accurately track family membership and our suspicion that multiples per family would be a rare occurrence, randomization of multiple FDRs per family was allowed.

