8. EFFICACY EVALUATIONS

8.1. Overview of Efficacy Analysis Methods

8.1.1. Multicenter Studies

Study participants were consented at 15 study sites. The analyses of survival estimates at fixed points in time will not be stratified. Site and method of recruitment will be considered as possible fixed covariates in models for secondary efficacy analyses. All safety analyses will be based on pooled data with no adjustment or stratification.

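### Should the secondary Cox models also adjust for smoker status, the third minimisation factor?

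*SAP*

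**What the plan says.** SAP 7.2 states: "The factors used in the adaptive randomization procedure were smoker status (smoker vs. non-smoker), study site, and method of recruitment". Protocol 3.1.1 gives the purpose, which is to "increase the likelihood of balance between treatment arms on key factors associated with progression to clinically-apparent RA".

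For the adjusted treatment effect on timing, SAP 8.3.3 (Table 11, Secondary 4.2, clinically-apparent RA) and SAP 8.3.4 (Table 12, Secondary 5.2, inflammatory arthritis) use the same sentence: "A Cox proportional hazards model will be fit with covariates for site (Colorado vs. other sites) and method of recruitment, along with treatment interactions". Interactions stay only if p<0.05. Smoker status is not in either model.

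Protocol 8.5.2 had already set the covariates: "Site and method of recruitment will be included as fixed covariates in models for secondary efficacy analyses". SAP 8.1.1 is looser: "Site and method of recruitment will be considered as possible fixed covariates in models for secondary efficacy analyses". Protocol 8.3.1.2 is looser still: "The two arms will also be compared after control of appropriate covariates using a Cox proportional hazards model". Its next sentence extends the modelling of RA or IA onset to baseline and environmental factors. Protocol 8.5.1 allows subgroups that turn out unevenly distributed between arms to be considered as Cox covariates.

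Smoking appears in two other places. SAP 6.2 tabulates it by arm. SAP 8.3.5 (model 6.1, clinically-apparent RA only) lists it as a candidate risk factor under this rule: "Risk factors with p-values <0.1, and interaction terms with p-values <0.05 will be considered for the final model".

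SAP 8.1.4 treats all secondary efficacy analyses as descriptive.

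**The concern.** The usual advice is to analyse as you randomise: a factor used to balance allocation belongs in the adjusted model. There are two reasons. A test that ignores a prognostic balancing factor tends to be conservative. And in a Cox model, leaving out a prognostic covariate pulls the treatment hazard ratio towards 1 even when the arms are perfectly balanced.

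Here one of three factors is missing without explanation. Model 6.1 does not reliably fill the gap. It selects by p-value, codes smoking in three levels rather than the two used in allocation, and has no counterpart for inflammatory arthritis. The SAP also records that assignments are unmasked before database lock, so a covariate set with no stated rationale invites questions. At stake is the accuracy of the two planned adjusted hazard ratios. The primary test is a fixed-time Kaplan-Meier comparison without covariates and is not affected.

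**Working it through.** **The plan's own figure.** Protocol 8.1 gives 90% power for the primary test with 80 per arm and RA-free survival of 50% vs 75%. On the logit scale the difference is ln(0.75/0.25) - ln(0.5/0.5) = 1.099. Its variance is 1/(80×0.5×0.5) + 1/(80×0.75×0.25) = 0.0500 + 0.0667 = 0.1167, so the SE is 0.342. Then 1.099/0.342 - 1.96 = 1.26, giving 89.6% power. The stated figure reproduces. No power is stated for the Cox models.

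**Information in the Cox model.** 144 were randomised (Interim SAP 5.2.2.1), taken as 72 per arm. Protocol 8.1 gives hazards of 0.231 and 0.096 per year. A 20% loss over 3 years, treated as exponential, is a hazard of -ln(0.8)/3 = 0.0744. Expected events per arm = 72 × λ/(λ+0.0744) × (1 - S×0.8), where S is 36-month RA-free survival.
- Placebo: 72 × 0.756 × 0.6 = 32.7
- HCQ: 72 × 0.563 × 0.4 = 16.2
- Total: 48.9

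Model 4.2 starts with up to 7 terms: treatment, site, two for recruitment and three interactions. That is 48.9/7 = 7.0 events per term. One more term makes it 48.9/8 = 6.1.

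**Effect of adding smoker status.** The documents give no smoking prevalence, smoking effect or IA risks, so these are assumed. Main simulation: 6,000 trials per setting; minimisation on smoker status, 15 sites and three recruitment groups with a 0.8 biased coin; 36-month risks of 50% vs 25% (CL-RA) and 60% vs 35% (IA); 20% loss; site and recruitment not prognostic; interactions dropped one at a time until all have p<0.05. Percentage of trials rejecting:

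| Setting | As planned | Smoker added |
|---|---|---|
| CL-RA, smoking not prognostic | 84.6 | 84.7 |
| CL-RA, smoker HR 1.5, 20% smokers | 85.0 | 85.5 |
| CL-RA, smoker HR 2.0, 10 / 20 / 30% smokers | 84.8 / 85.9 / 85.4 | 85.2 / 86.6 / 86.6 |
| IA, 20% smokers, smoker HR 1.5 / 2.0 | 84.2 / 83.9 | 85.0 / 85.7 |
| No treatment effect, CL-RA, smoker HR 1.5 / 2.0 | 5.50 / 4.78 | 5.90 / 5.60 |
| No treatment effect, IA, smoker HR 2.0 | 4.95 | 5.58 |

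The larger model also rejects more often when there is no effect. With both tests held at 5%, the change in power is -0.30 (CL-RA, HR 1.5), -0.22 (CL-RA, HR 2.0) and +0.50 points (IA, HR 2.0). Monte Carlo SEs are 0.17 to 0.24, before allowing for error in the critical values. A separate run of main-effects models, 20,000 trials per setting, agrees: 84.7 vs 84.5% at smoker HR 1.5, 83.5 vs 83.3% at HR 2 with 20% smokers, and 81.3 vs 81.7% at HR 3. Its rejection with no effect rises from 4.3-4.9% to 5.3-5.6%.

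**Effect on the estimate.** The SE of the log HR for CL-RA is 0.313 as planned and 0.314-0.315 with smoker status. The mean shift in log HR is 0.02 at smoker HR 1.5 and 0.03-0.04 at HR 2.0. Relative to the SE that is 0.02/0.313 = 0.06 to 0.04/0.313 = 0.13. Median HRs at smoker HR 2.0 with 20% smokers:

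| Endpoint | True conditional HR | As planned (error) | Smoker added (error) |
|---|---|---|---|
| CL-RA | 0.407 | 0.404 (0.003) | 0.394 (0.013) |
| IA | 0.459 | 0.464 (0.005) | 0.452 (0.007) |

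The planned model is nearer in both. With about 49 events the larger model slightly overshoots, and here the attenuation from leaving smoking out is no worse than that overshoot.

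**The case for a change.** The strongest case for a change is that the sponsor itself chose smoker status as a balancing factor, and Protocol 1.1.4 names tobacco smoke as the strongest environmental exposure. If smoking mattered a great deal, the omission would show more. In a further main-effects run (3,000 trials per setting, true HR 0.415) with smoker HR 3 and 30% smokers, the planned model gave a mean HR of 0.430 against 0.401 with smoker status. Nominal power was 81.6% against 85.0%, and rejection with no effect was 3.9% against 5.4%. Adding the term costs one coefficient on data already collected.

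Part of this stands: the omission is real and unexplained. The rest weakens on inspection. Even in that setting the two estimates miss 0.415 by almost the same amount (0.015 and 0.014), and at equal test size the power gap at smoker HR 3 is 81.3 vs 81.7%. The protocol is also doubtful about a strong effect in this antibody-selected population. Protocol 1.5.4 finds "not clear data to date that evaluating genetic and environmental factors adds substantial predictive power to future RA beyond that of anti-CCP positivity", although it says so when discussing entry criteria.

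Timing favours the plan as written. Protocol v3.0 of 1 May 2020 named site and recruitment method. The SAP was signed on 12 May 2023, after the April 2022 futility interim, with assignments to be unmasked before lock. At that point, keeping the protocol's covariates is easier to defend than adding one. Only the Colorado-versus-other coding is new, and it is sensible: 15 sites would need 14 terms on about 49 events.

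**Conclusion.** No change is needed. The SAP follows the protocol's covariate rule, so the two documents do not conflict on smoker status. The planned models are valid for this purpose. Leaving smoker status out moves the log hazard ratio by about 0.02 to 0.04 (2-4%) towards 1 if smoking has a hazard ratio of 1.5 to 2.0. The 95% interval spans a factor of exp(1.96×0.313) = 1.85 either side of the estimate. Adding the term yields no clear power at equal size and no smaller SE, and the estimate is no nearer the truth. What remains is convention, and it does not outweigh keeping covariates fixed before the interim in descriptive analyses of a trial stopped for futility.

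The size rests on assumed smoking prevalence (10-30%), smoking hazard ratio (1.0-2.0, with 3 as an extreme), IA risks and coin probability. Minimisation itself left a mean smoker imbalance of only 1.5-1.6 percentage points in the main simulation.

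The missing reason is a gap that one sentence in the report can fill. The difference in wording between SAP 8.1.1 and Protocol 8.5.2 is editorial, because SAP Tables 11 and 12 already fix the covariates for these two models.
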